6.5.2 Baseline Assessments

Once informed consent is given and it is confirmed that the participant meets all inclusion and exclusion criteria, baseline data will be collected. These include: Baseline Health Status and Demographic Information.

Stools will be collected multiple times throughout the study. Research staff will be trained on how to properly transport stool and how to instruct participants on collecting stool.

During the initial visit, participants will also be given all materials to collect stools, the diary, and study materials as well as the initial compensation. The participant will commence the 30-day run-in period. During this 30-day run-in period, the participant will refrain from antibiotics and probiotics (a "What Not to Eat list will be provided) and provide two baseline stool samples--one pre run-in, and one post run-in (prior to starting the yogurt and antibiotics).

Additionally, the research staff will phone the participant two times during the run-in period to collect 24-hour diet recall data. The instrument, the Automated Self-Administered 24-Hour (ASA24®) Dietary Assessment Tool, will be administered by the research staff and recorded for one weekday and one weekend day (<https://epi.grants.cancer.gov/asa24/>).

Following the run-in period and prior to the yogurt start day (day 1), research staff will contact the participant in order to complete the Post Run-in Health Status form and repeat the Inclusion/Exclusion form to ensure that the participants are still eligible. Participants who start an exclusionary medication or experience an onset of an exclusionary, nontransient health condition from the time of enrollment will be withdrawn from the study.

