9.2 Sample Size and Randomization

Sample size calculations were informed by data from Hoverstad et al.,(120, 121) which compared changes in the mean SCFA levels between baseline fecal samples and fecal samples collected after six days administration of various antibiotics or placebo in healthy volunteers. In these studies, a mean reduction in acetate levels occurred from 45 ± 16 umol/g at baseline to 24 ± 18 umol/g after antibiotic treatment (46% reduction in acetate). Reductions in acetate after antibiotic treatment ranged from 5% to 79% with ampicillin, a similar antibiotic to amoxicillin.(120, 121) We can infer similar decreases in acetate in our proposed study. Using a conservative estimate of a 42% decrease in acetate in the control/antibiotic treated group and no greater than a 15% decrease in the BB-12 treated group, and an allocation ratio of 2:1 (BB-12 to control volunteers); a total sample size of 60 participants is necessary to have 80% power to detect a significant difference in mean acetate levels as a measure of gut microbiota production of SCFA between a control and BB-12-treated group.

With a sample size of 40 subjects in the active arm and 20 subjects in the control arm and attrition rate of 5% at day six and 20% at day 30, we would have power of 82% to detect a moderate effect size of Cohen's $d = 0.63$ (assuming the intra-correlation correlation coefficient is 0.3). The α level of 0.05 will be used for the analysis. Since the effect size of previous study (reduction in acetate levels) is Cohen's $d = 1.23$, we should have ample power to detect the treatment effect. (The power calculation is based on the R software and packages simr, sjstats, and pwr).

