9.6 Anticipated Results

The most likely outcomes from the study are:

1. +/- impact of BB-12 on fecal SCFA levels
2. +/- impact of BB-12 on gut microbiota composition (measured to quantify level of disruption achieved by antibiotics as a comparator within this study)
3. +/- impact of BB-12 on AAD (measured, but study not powered to detect clinical difference of AAD).

If BB-12 is found to have a positive effect on the biological signature (acetate levels) as compared to the control, the work to be carried out in the R33 will replicate the R61 methods in a second cohort of

patients, with the addition of timing of probiotic administration, as well as expanding the analysis to characterize the functional microbiome using metatranscriptomic methods. This information will provide a framework for future research in the characterization of other probiotic strains for AAD.

Negative overall group results, i.e. no significant difference between the control and BB-12 groups with respect to longitudinal changes in acetate levels and microbiome composition versus baseline values, will suggest that BB-12 does not impact the gut environment via the mechanisms we hypothesized. However, based on past studies of AAD and BB-12, it is unlikely that we will see no responders to this natural product. However, based on past studies of AAD and BB-12, it is unlikely that we will see no effect of the BB-12 probiotic on maintenance of acetate levels when administered concurrently with antibiotic. Thus, we intend to correlate the changes in acetate levels, by examining the highest and lowest quartiles over time in study participants receiving probiotic to assess whether we can predict the impact of BB-12 using the baseline. Such results will enable fine-tuning of conclusions based on individual responses and suggest new hypotheses for future studies.

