9.7 Data Analyses

To examine the primary hypothesis that BB-12 supplementation will protect against antibiotic-induced SCFA reduction, the mixed model will be used to analyze the treatment effect on the antibiotic-induced SCFA reduction. Statistical analyses will be performed using intent-to-treat analytic strategies. The mixed effect model will be used, which is compatible with unbalanced outcome measurements. The change of SCFA from baseline will be considered as the outcome variable of the mixed model. All time points will be included for the analysis. Covariates including age, sex, BMI and time (a continuous variable) will be adjusted when necessary. In addition, the time and treatment interaction term will be assessed by the likelihood ratio test. The random intercept will be used and the AR1 and/or compound symmetry covariance structure will be considered (and then the likelihood test can help to determine the more appropriate covariance structure). The final model selection will be performed based on information criteria such as Akaike information criterion (AIC) or Bayesian information criterion (BIC). Power: with a sample size of 40 subjects in the treatment arm and 20 subjects in the placebo arm and attrition rate of 5% at day six and 20% at day 30, we would have power of 82% to detect a moderate effect size of Cohen's $d = 0.63$ (assuming the intra-correlation correlation coefficient is 0.3). The α level of 0.05 will be used for the analysis. Since the effect size of previous study (reduction in acetate levels) is Cohen's $d = 1.23$, we should have ample power to detect the treatment effect. (The power calculation is based on the R software and packages simr, sjstats, and pwr).

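### Section 9.6 relates acetate change to baseline within the BB-12 arm only; if baseline acetate is meant, an ordinary test will often find a predictor of response where none exists

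*Combined protocol and SAP*

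**What the plan says.** Section 9.6 (Anticipated Results) first describes what a negative group result would mean. It then says the investigators intend to correlate the changes in acetate "by examining the highest and lowest quartiles over time in study participants receiving probiotic to assess whether we can predict the impact of BB-12 using" what it calls the baseline. The results are meant to refine conclusions at the level of individual responses and to generate hypotheses.

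The section names no test, null value or alpha, does not say which variable defines the quartiles, and does not define the baseline further. The analysis is restricted to probiotic recipients.

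Section 9.7 (Data Analyses) confirms that acetate is analysed as a change score: "The change of SCFA from baseline will be considered as the outcome variable of the mixed model". Its model adjusts for age, sex, BMI and time and considers a time-by-treatment interaction. No baseline-by-treatment interaction is planned. Neither section mentions regression to the mean or the dependence of a change score on its own baseline.

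**The concern.** Change is later acetate minus baseline acetate. When it is related to baseline acetate, the same measurement stands on both sides with opposite signs. A participant whose baseline stool happened to be high tends to show a large fall, and one whose stool happened to be low tends to look protected. A test against zero association picks up this arithmetic and regression to the mean, whether or not the effect of BB-12 depends on baseline.

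The one-arm restriction adds a second problem. Every participant takes amoxicillin-clavulanate, so even a real relation between baseline and change among BB-12 recipients could belong to the antibiotic. The control arm would show the same slope.

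At stake is the interpretation of a null trial. It could still report that participants with low baseline acetate respond to BB-12, and that claim could shape later studies.

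**Working it through.** **Inputs.** Section 9.2 gives acetate as falling "from 45 ± 16 umol/g at baseline to 24 ± 18 umol/g after antibiotic treatment (46% reduction in acetate", so s0 = 16 and s1 = 18. It gives one within-person correlation, "assuming the intra-correlation correlation coefficient is 0.3". Using this as the correlation rho between baseline and day-7 acetate is an assumption, so a range is shown. The BB-12 arm has 40 participants with "attrition rate of 5% at day six and 20% at day 30", which leaves 40 × 0.95 = 38 early and 40 × 0.80 = 32 at day 30. Alpha is 0.05, taken as two-sided.

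**Check of the SDs.** d = (45 − 24)/√((16² + 18²)/2) = 21/17.03 = 1.23. This matches the effect size stated in Section 9.2.

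**Expected correlation when BB-12 shifts everyone by the same amount.**

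corr(change, baseline) = (rho·s1 − s0)/√(s0² + s1² − 2·rho·s0·s1)

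At rho = 0.3: (5.4 − 16)/√(256 + 324 − 172.8) = −10.6/20.18 = −0.525.

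**How often a 5% test rejects.** Hand check by Fisher's transformation at n = 38: atanh(0.525) × √35 = 3.45, so power against zero is about P(Z > 1.96 − 3.45), or 93%. Simulation of 20,000 BB-12 arms with a constant effect gives 94%. A t-test between extreme quartiles gives 84%, whether the quartiles are formed on baseline or on change. With n = 32 the figures are 89% and 77%.

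| rho (assumed) | Expected correlation | Correlation test, n = 38 | Extreme quartiles, n = 38 |
|---|---|---|---|
| 0 | −0.66 | 99.7% | 98% |
| 0.3 | −0.52 | 94% | 84% |
| 0.5 | −0.41 | 74% | 60% |
| 0.6 | −0.34 | 57% | 44% |
| 0.7 | −0.26 | 35% | 27% |
| 0.8 | −0.15 | 14% | 12% |
| 0.9 | 0.03 | 5% | 5% |

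Rejection falls below half at rho of about 0.63 (correlation) or 0.56 (quartiles).

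**Size of the artefact.** At rho = 0.3 the slope of change on baseline is 0.3 × 18/16 − 1 = −0.66. The lowest and highest baseline quartiles then differ by about 27 umol/g in change with no effect modification at all.

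**If a baseline microbiome marker is meant.** At rho = 0.3, with the marker related to day-7 acetate only through baseline acetate, the correlation test rejects in 5%, 10% and 25% of trials when the marker correlates 0, 0.2 and 0.4 with baseline acetate.

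**Baseline-by-arm interaction, both arms (38 and 19).** With a constant effect both arms have the same slope, and the interaction test rejects in 5.0%, 4.8% and 5.0% of trials at rho 0.3, 0.5 and 0.7. Its power at rho = 0.3 is 34% for a true slope difference of 0.5 and 64% for 0.75.

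**Pre-run-in stool as predictor, change measured from the post-run-in stool.** The expected correlation is (r_pre,7 × 18 − r_pre,post × 16)/20.18 when the post-run-in stool correlates 0.3 with day 7. If all three stools correlate 0.3, this is (5.4 − 4.8)/20.18 = 0.03 and rejection is about 5%. If the two baseline stools correlate 0.5 or 0.7 with each other but 0.3 with day 7 (assumed values), it is (5.4 − 8)/20.18 = −0.13 or (5.4 − 11.2)/20.18 = −0.29, and rejection is about 12% or 42%.

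**The case against.** **The analysis is loosely described and may be only descriptive.** This is fair. No test is named, and the same paragraph also mentions microbiome composition, so baseline acetate is a reading, although acetate is the only variable in that sentence. The error rates apply only if an ordinary test against zero is used. But correlating changes and comparing extreme quartiles both lead naturally to such a test, and nothing in the plan prevents it.

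**The size depends on rho.** This also stands. The ICC of 0.3 is a power input for the mixed model, and the documents do not say it is the raw baseline-to-day-7 correlation. A reader might infer that most trials would produce a false predictor whatever the data look like. That holds only up to a correlation of about 0.56 to 0.63, and at 0.9 there is no inflation.

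**It is exploratory.** True. A reader might infer that the primary result or the R33 decision is compromised. Neither uses this analysis: Section 9.5.1 defines a between-arm difference and the milestone in Section 9.1 is a between-arm effect size. Using change as the outcome in the between-arm model of Section 9.7 does not have this defect.

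**A second baseline stool exists.** Participants "provide two baseline stool samples--one pre run-in, and one post run-in (prior to starting the yogurt and antibiotics"). One might infer that using the pre-run-in stool as predictor settles the matter. It does so only if the two antibiotic-free stools correlate no more with each other than with the day-7 stool. That is doubtful, because Section 9.2 reports acetate reductions from 5% to 79% under ampicillin. Nor would it separate BB-12 from the antibiotic.

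**Conclusion.** The concern holds in conditional form. If the baseline in Section 9.6 is baseline acetate and the association is tested against zero, the planned analysis cannot show whether baseline predicts the impact of BB-12. On the plan's own SDs, with its ICC taken as the baseline-to-day-7 correlation and 38 participants, the false-positive rate is about 94% (correlation) or 84% (extreme quartiles) instead of 5%. Over assumed correlations from 0 to 0.9 it runs from nearly 100% down to nominal. For a baseline microbiome marker the range is about 5% to 25%.

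The calculations assume normal data and a BB-12 effect that is the same shift in umol/g for everyone. The consequence is confined to an exploratory analysis, but one that the plan gives a role in qualifying a negative group result. It should be corrected before the data are analysed.

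**What to change.** In Sections 9.6 and 9.7, replace the extreme-quartile analysis of BB-12 recipients with a model that uses both arms, enters baseline acetate as a continuous covariate and tests the baseline-by-arm interaction. Name the baseline sample and the scale (absolute or log), because a constant percentage effect is not a constant shift in umol/g. Add that a within-arm association between change and the baseline value that defines it will not be read as prediction of BB-12 response.

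This costs a few sentences and needs no new data. The drawback is limited power: about 34% to 64% for slope differences of 0.5 to 0.75. The plan should say so and report the interaction with its confidence interval, so that a non-significant result is not taken as absence of effect modification.

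The pre-run-in stool can serve at most as the predictor in a sensitivity analysis. Table 8, as far as its columns can be read, marks SCFA testing at one pre-intervention time only, so this may need an extra acetate assay per participant.

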3. STUDY DESIGN

In order to determine the ability of BB-12 to impact antibiotic-induced perturbation and recovery, we will conduct a randomized, double-blinded, controlled trial in **60 healthy participants**, ages 18-65 years. The full inclusion and exclusion criteria are listed in Section 4.1. All participants will be given a 7-day prescription for 875/125 mg of amoxicillin-clavulanate (AMC), taken twice daily. In order to control for confounding by disease state and specific antibiotic used, all participants will receive the same daily dose --a four-ounce (approximately 100 ml) serving of probiotic (which delivers $\geq 10^{10}$ CFU of BB-12) or control yogurt-- and length of antibiotic treatment after a 30-day run-in period.

Participants are to provide informed consent on at Baseline, complete the 30-day run-in --during which they will refrain from all probiotics-- and begin the antibiotic and yogurt interventions on Day 1. As with our previous studies, enrollment and informed consent will occur at a private location, either in [name] laboratory at Georgetown University Medical Center, or at the participant's home, as per the participant's preference. All interventions will be delivered in coolers to the participants' homes prior to day 1, at a time of their choosing.

Participants will be randomized to receive BB-12-supplemented yogurt and non-supplemented control yogurt (without BB-12), in a 2:1 (40:20 participants) allocation (**Figure 1**). Participants of all ages will consume the same dose of product per day for 14 days, at the same time as the AMC.

Fecal samples will be collected at home (twice at baseline (pre-run-in and post-run-in), and on days 7, 14, 21 and 30) into a maximum of three (1 sample for SCFA, 1 sample for microbiome testing, and 1 sample for potential future analysis) sterile, screw-capped tubes and frozen within one hour of collection in a home freezer. Participants will be given detailed, written and illustrated instructions on proper sample collection procedures, using protocols from the [name] laboratory and as described in previous studies. Research staff will review these protocols with participants during enrollment. Immediately after collection and freezing, a member of the research team will be alerted to retrieve and transport the samples to the laboratory. The samples will be stored at -80°C until transport to The IGS. All staff will receive certification on handling procedures.

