The mechanism of prebiotics works primarily through their main fermentation pathway, in which the gut generates pyruvate from hexoses in the undigested carbohydrates. Gut bacteria use a range of carbohydrate hydrolysis enzymes to produce hydrogen, methane, carbon dioxide, short-chain fatty acids (SCFAs), and lactate [7]. Specifically, SCFAs are an important product of this mechanism because of their many significant contributions to human health, including nourishing cells that line the gut, enhancing Ca⁺ absorption, relieving constipation and diarrhea, as well as entering the bloodstream and traveling to other organs, and in doing so, act as signals to communicate with the brain and regulate the immune system and inflammation [7].

For this substudy, we aim to use the existing data to explore the effect that a participant's dietary fiber intake has on the occurrence of adverse events related to undergoing a 7-day course of antibiotics. No new data will be collected. Additionally, this substudy seeks to examine if higher consumption of dietary fiber impacts the effect of antibiotic-induced reduction in SCFA concentration as reflected by the levels of acetate in stool samples. The primary hypothesis of this substudy is that a higher intake of dietary fiber will result in participants experiencing fewer adverse events from the antibiotic. Further, this substudy's secondary hypothesis is that a higher intake of dietary fiber will result in less of a reduction in SCFAs by day 7, as well as a quicker return to baseline SCFA.

References:

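### Section 9.6 seeks baseline predictors of the impact of BB-12 among BB-12 recipients with no control comparison named, so it can find only correlates of acetate change under antibiotic plus BB-12

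*Combined protocol and SAP*

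**What the plan says.** Section 9.6 considers what follows if the groups do not differ in acetate or microbiome change. It first says that such a result would count against the hypothesized mechanisms. It then calls a complete absence of effect unlikely and plans to compare the two extreme quarters of acetate change "in study participants receiving probiotic to assess whether we can predict the impact of BB-12 using the baseline". Two uses are given for the output: new hypotheses, and "Such results will enable fine-tuning of conclusions based on individual responses". The section does not name the baseline variable, the scale of change or the test.

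No other section supplies the missing contrast. In Section 9.7, "the time and treatment interaction term will be assessed by the likelihood ratio test"; this is the only interaction planned there, and age, sex and BMI enter as adjustment covariates. Section 6.2.1.4 plans correlations of microbiota members with clinical outcomes, and the secondary analysis under Section 9.8 looks at treatment effects on microbiota scores. None of these is a baseline-by-treatment analysis. Section 6.5.3 says that control participants go through the same stool collection and follow-up as the BB-12 group.

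**The concern.** The impact of BB-12 on a participant is the difference between that participant's acetate course with BB-12 and without it, the antibiotic being given in both cases. In the BB-12 arm only the first course is seen. A feature that separates large from small acetate falls there may do so because it governs the response to the antibiotic, because it governs benefit from BB-12, or both. The control arm is what tells these apart.

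The misreading is most tempting where the plan places the step: after a null comparison, with the result allowed to adjust conclusions by individual response. A marker of resilience to the antibiotic could be reported as identifying BB-12 responders, and later work could be built on the wrong quantity.

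Dietary fiber is one possible illustration. Substudy Addendum A hypothesizes that "a higher intake of dietary fiber will result in less of a reduction in SCFAs by day 7", without reference to arm, and under Section 6.5.2 "the research staff will phone the participant two times during the run-in period to collect 24-hour diet recall data". If that hypothesis were true and BB-12 did nothing, fiber would still separate the extreme quartiles in the BB-12 arm.

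**Working it through.** The plan gives no sample size, power or error rate for this step, so there is no figure to reproduce.

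**Structure.** Let *m* be a standardized baseline feature, *g* its slope on acetate change under the antibiotic alone, and *h* the extra slope if it modifies the BB-12 effect.

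- Control arm slope: *g*
- BB-12 arm slope: *g* + *h*
- Difference between arms: (*g* + *h*) − *g* = *h*

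The BB-12 arm alone estimates *g* + *h*. No sample size separates the two terms without the control slope.

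**Inputs from the documents.** 40 BB-12 and 20 control participants (Section 6.5.3); acetate 45 ± 16 before and 24 ± 18 umol/g after antibiotic, and alpha 0.05 (Section 9.2). **Assumed:** two-sided testing; BB-12 inert (*h* = 0); 10 participants in each extreme quartile of change; a t-test comparing the feature between those quartiles; normal data; the correlations shown.

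**A purely prognostic feature (simulation).**

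| Correlation with change, both arms | Flagged, BB-12 arm quartiles | Flagged, two-arm interaction |
|---|---|---|
| 0 | 5% | 5% |
| 0.3 | 37% | 5% |
| 0.4 | 61% | 5% |
| 0.5 | 83% | 5% |

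Hand check at 0.3. The simulated gap in the feature between extreme quartiles is 0.75 SD. Taking the SD within a quartile as just under 1 (0.965), the noncentrality is 0.75 / (0.965 × √(2/10)) = 1.74, which on 18 degrees of freedom gives power of about 37%. The inert control arm shows nearly the same gap, 0.73 SD, so a side-by-side display would reveal that the pattern is not specific to BB-12.

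**Baseline acetate as the feature.** If change is absolute, baseline is part of the change score. With baseline-to-day-7 correlation ρ,

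corr(baseline, change) = (ρ·16·18 − 16²) / (16·√(16² + 18² − 2ρ·16·18)).

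At ρ = 0.3: (86.4 − 256) / (16 × √407.2) = −169.6 / 322.9 = −0.53. With BB-12 inert, the quartile test flags baseline acetate in 87%, 63% and 28% of trials at ρ = 0.3, 0.5 and 0.7; the interaction stays at about 5%. On percent or log change the effect is smaller and irregular (21–22%, 5%, 26–27%, with lognormal data).

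The problem is not confined to acetate. A feature that correlates 0.7 with baseline acetate, and relates to day 7 only through it, has correlation 0.7 × (−0.53) = −0.37 with absolute change.

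**Scale for the interaction.** With skewed (lognormal) acetate and a prognostic feature, the interaction keeps its level on the log scale (4.8–5.2%). On absolute or percent change it is flagged in 5.8–8.3% of trials by ordinary least squares and 4.0–4.7% with robust (HC3) errors.

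**Precision of the interaction at 40:20.** For a standardized feature with *g* = 0.3, the large-sample standard error is √(0.91 × (1/40 + 1/20)) = 0.26; in simulation it is 0.28, giving a 95% interval of about ±0.55. Power is about 30% at *h* = 0.4 and 81% at *h* = 0.8.

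**The case against.** The strongest reply concerns weight. Section 9.6 is a narrative of anticipated results and the formal analyses are in Section 9.7. The step names no test, is partly for new hypotheses, and follows a sentence that already draws the negative conclusion from a null group result. It feeds neither the primary analysis nor the R33 milestone in Section 9.1. All of that stands and keeps the point small. It does not remove it, because the same paragraph also allows the results to adjust conclusions.

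The section does not say that control participants are excluded, and Section 3.2 shows that the authors know what the control arm is for. That is fair. The supported statement is that 9.6 names one population and no control comparison.

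Three stronger readings are tempting, and the documents do not support them.

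- A reader might infer that the plan intends to use fiber as a predictor of BB-12 benefit. Section 9.6 never mentions diet, and Addendum A claims nothing about BB-12 impact.
- A reader might take the statement in Section 9.2, "Reductions in acetate after antibiotic treatment ranged from 5% to 79% with ampicillin", as a reason to expect baseline predictors. It shows spread. It does not say whether the range is across individuals or groups, and spread need not be predictable.
- A reader might take 37% to 83% as this trial's false-positive rate. These are the chances that a test the plan does not name detects a real prognostic correlation whose size is assumed.

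The low power of the interaction also stands as an objection. It argues for showing the estimate with its interval. It does not justify using a BB-12-arm contrast that measures something else.

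**Conclusion.** The point holds, with low weight. Read as written, the Section 9.6 analysis would attach the label of BB-12 impact to a quantity that mixes antibiotic response with BB-12 benefit. That follows from the design and needs no assumed figure. The size does: 37% to 83% rests on an inert BB-12, correlations of 0.3 to 0.5 shared by both arms, and a t-test on 10 against 10. The documents give no such correlation, so confidence is high in the principle and limited in the magnitude. Baseline acetate, or anything correlated with it, adds regression to the mean when change is absolute. Nothing here bears on the primary comparison or on the decision to move to R33.

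**What to change.** Amend Section 9.6 as follows.

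- Run the same analysis in both arms and show the control quartiles beside the BB-12 quartiles.
- Report the treatment-by-baseline interaction, with baseline continuous and both main effects in the model, as an estimate with its confidence interval. Label it exploratory and do not use significance as a gate.
- Use log acetate, or robust standard errors if change is absolute or percent.
- Name the baseline variable or variables and the scale of change in advance. Also state which baseline sample is used, since Section 3 collects stool "twice at baseline (pre-run-in and post-run-in), and on days 7, 14, 21 and 30".
- Do not describe a feature as predicting the impact of BB-12 from BB-12-arm data alone. Call it a correlate of acetate change under antibiotic plus BB-12.

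The cost is some wording and one exploratory model on samples already planned in both arms. The downside is imprecision: an interval of about ±0.55 for a standardized feature, and only 5 control participants in each extreme quartile (20 / 4).
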